6.7. Intervention after the End of the Study

Not applicable.

7. DISCONTINUATION OF STUDY INTERVENTION AND PARTICIPANT DISCONTINUATION/WITHDRAWAL

[figure not shown]
7.1. Discontinuation of Study Intervention

In rare instances, it may be necessary for a participant to permanently discontinue study intervention. If study intervention is permanently discontinued, the participant will remain in the study and followed appropriately until resolution of the event or return of labs to acceptable levels. See the SOA for data to be collected at the time of discontinuation of study intervention.

7.1.1. Liver Chemistry Stopping Criteria

Study intervention will be discontinued for a participant if liver chemistry stopping criteria are met:

Phase I Liver Chemistry Stopping Criteria – Liver Stopping Event Algorithm

Abbreviations: ALT = alanine transaminase; INR = international normalized ratio; SAE = serious adverse event; ULN = upper limit of normal.

Liver Safety Required Actions and Follow up Assessments Section can be found in [Appendix 6](#)

Liver chemistry stopping and increased monitoring criteria have been designed to assure participant safety and evaluate liver event etiology.

Discontinuation of study intervention for abnormal liver tests is required when:

- a participant meets one of the conditions outlined in the algorithm
- OR
- when in the presence of abnormal liver chemistries not meeting protocol-specified stopping rules, the investigator believes study intervention discontinuation is in the best interest of the participant.

7.1.1.1. Study Intervention Restart or Rechallenge after liver stopping criteria met

Study intervention restart or rechallenge after liver chemistry stopping criteria are met by any participant in this study is not allowed.

7.1.2. QTc Stopping Criteria

- The QTcF formula *must* be used for *each individual participant* to determine eligibility for and discontinuation from the study. This formula may not be changed or substituted once the participant has been enrolled.

- For example, if a participant is eligible for the protocol based on QTcF, then QTcF must be used for discontinuation of this individual participant as well.
- The QTcF formula must be used for a participant *for all QTc data being collected for data analysis*. Safety ECGs and other non-protocol specified ECGs are an exception.
- The QTc should be based on the average of triplicate ECG readings obtained over a brief (e.g., 5-10 minute) recording period.

A participant that meets either bulleted criterion based on the average of triplicate ECG readings will be withdrawn from study intervention.

- QTcF >500 msec,
- Change from Baseline: QTc >60 msec

See the SoA for data to be collected at the time of intervention discontinuation and follow-up and for any further evaluations that need to be completed.

7.1.3. Individual Stopping Criteria

- Any participant who experiences an SAE will be withdrawn from the study.
- Any participant who experiences an AE of moderate or severe intensity (as defined in CTCAE v5.0) that is considered attributable to dosing with GSK3439171A will be withdrawn from the study.

7.1.4. Dose Adjustment/Discontinuation Pharmacokinetic Criteria

In part A, any participant with observed AUC(0-inf) or C_{max} values greater than the mean steady-state AUC(0-24) and C_{max} values in male dog (57.8 µg·h/mL and 10 µg/mL, respectively) will be discontinued from study intervention.

In Part B, any participant with observed AUC(0-24) value greater than the mean steady-state AUC(0-24) observed in female dogs (11.0 µg·h/mL) will be discontinued from study intervention.

See the SoA for data to be collected at the time of treatment discontinuation and follow-up and for any further evaluations that need to be completed.

7.1.5. Temporary Discontinuation

Temporary discontinuation of the study intervention is not allowed.

7.1.6. Study Stopping Criteria

7.1.6.1. Safety Study Stopping Criteria

Dosing at the currently tested dose as well as escalation to higher doses will be stopped if either of the following occurs in the current dose group:

- An SAE that is considered to be related to GSK3439171A in one or more participants on active treatment.
- Similar AEs of moderate or severe intensity (as defined in CTCAE v5.0) that are considered to be related to GSK3439171A in two or more participants on active treatment.

Dosing at the current (or higher) dose may resume only if a safety review conducted by GSK in conjunction with the investigator determines that the observed SAEs or AEs are not related to GSK3439171 and such resumption is approved by the IRB/IEC.

7.1.6.2. PK Study Stopping Criteria

The single dose PK stopping criteria are based on AUC(0-24) from the 600 mg/kg/day male dog due to liver findings. It is planned that for Part A, the predicted human mean GSK3439171A AUC(0-inf) or Cmax values will not exceed the mean GSK3439171A steady-state AUC(0-24) and Cmax values in male dog (57.8 ug·h/mL and 10 ug/mL, respectively).

The repeat dose PK stopping criteria are based on AUC(0-24) from the 20 mg/kg/day female dog NOAEL due to liver findings. It is planned that for Part B, the predicted human mean GSK3439171A AUC(0-24), value will not exceed the mean GSK3439171A steady-state AUC(0-24) values in dog at 20 mg/kg/day of 11.0 ug·h/mL.

7.2. Participant Discontinuation/Withdrawal from the Study

- A participant may withdraw from the study at any time at his/her own request, or may be withdrawn at any time at the discretion of the investigator for safety, behavioral, compliance or administrative reasons. This is expected to be uncommon.
- At the time of discontinuing from the study, if possible, an early discontinuation visit should be conducted, as shown in the SoA. See SoA for data to be collected at the time of study discontinuation and follow-up and for any further evaluations that need to be completed.
- The participant will be permanently discontinued both from the study intervention and from the study at that time.
- If the participant withdraws consent for disclosure of future information, the sponsor may retain and continue to use any data collected before such a withdrawal of consent.
- If a participant withdraws from the study, he/she may request destruction of any samples taken and not tested, and the investigator must document this in the site study records.

7.3. Lost to Follow Up

A participant will be considered lost to follow-up if he or she repeatedly fails to return for scheduled visits and is unable to be contacted by the study site.

The following actions must be taken if a participant fails to return to the clinic for a required study visit:

- The site must attempt to contact the participant and reschedule the missed visit as soon as possible and counsel the participant on the importance of maintaining the assigned visit schedule and ascertain whether or not the participant wishes to and/or should continue in the study.
- Before a participant is deemed lost to follow up, the investigator or designee must make every effort to regain contact with the participant (where possible, 3 telephone calls and, if necessary, a certified letter to the participant's last known mailing address or local equivalent methods). These contact attempts should be documented in the participant's medical record.
- Should the participant continue to be unreachable, he/she will be considered to have withdrawn from the study.

Discontinuation of specific sites or of the study as a whole are handled as part of [Appendix 1](#).

8. STUDY ASSESSMENTS AND PROCEDURES

- Study procedures and their timing are summarized in the SoA.
- Protocol waivers or exemptions are not allowed
- Immediate safety concerns should be discussed with the sponsor immediately upon occurrence or awareness to determine if the participant should continue or discontinue study intervention.
- Adherence to the study design requirements, including those specified in the SoA, is essential and required for study conduct.
- All screening evaluations must be completed and reviewed to confirm that potential participants meet all eligibility criteria. The investigator will maintain a screening log to record details of all participants screened and to confirm eligibility or record reasons for screening failure, as applicable.
- Procedures conducted as part of the participant's routine clinical management (e.g., blood count) and obtained before signing of ICF may be utilized for screening or Baseline purposes provided the procedure met the protocol-specified criteria and was performed within the time frame defined in the SoA.
- The maximum amount of blood collected from each participant over the duration of the study, including any extra assessments that may be required, will not exceed 500 mL.
- Repeat or unscheduled samples may be taken for safety reasons or for technical issues with the samples.

8.1. Efficacy Assessments

Not applicable.

8.2. Safety Assessments

Planned time points for all safety assessments are provided in the SoA.

8.2.1. Physical Examinations

- A full physical examination will include, at a minimum, assessments of the Skin, Cardiovascular, Respiratory, Gastrointestinal and Neurological systems. Height and weight will also be measured and recorded (height is only measured at screening).
- A brief physical examination will include, at a minimum, assessments of the skin, lungs, cardiovascular system, and abdomen (liver and spleen).
- Investigators should pay special attention to clinical signs related to previous serious illnesses.

8.2.2. Vital Signs

- Oral temperature, pulse rate, respiratory rate, and blood pressure will be assessed.
- Blood pressure and pulse measurements will be assessed with a completely automated device. Manual techniques will be used only if an automated device is not available.
- Blood pressure and pulse measurements should be preceded by at least 5 minutes of rest in a supine position for the participant in a quiet setting without distractions (e.g., television, cell phones).
- Vital signs will be measured in a supine position after 5 minutes rest and will include temperature, systolic and diastolic blood pressure, and pulse and respiratory rate. Three readings of blood pressure and pulse will be recorded at intervals 1 to 2 minutes apart as specified in the SoA. The first reading should be rejected. The second and third readings should be averaged to give the measurement to be recorded in the case report form (CRF).

8.2.3. Electrocardiograms

- Triplicate 12-lead ECG will be obtained as outlined in the SoA (see Section 1.3) using an ECG machine that automatically calculates the heart rate and measures PR, QRS, QT, and QTc intervals. Refer to Section 7 for QTc withdrawal criteria and additional QTc readings that may be necessary.
- ECGs will be recorded whilst the participant is in a supine position, having rested in this position for at least 15 minutes. Participants are permitted to make intermittent movement, if necessary, in preparation for procedures (e.g., to sit up to take study medication). When ECGs are to be taken in triplicate, an interval of at least 5 minutes will be used between measures taken at screening or pre-dose. An interval of at least 1 minute is acceptable for any post-dose triplicate ECGs, when needed.

- Various values from the ECG read-out will be entered into the eCRF (the average for some will be used for measures made in triplicate).
- Any result falling outside the expected normal ranges as defined by the site will be repeated at the discretion of the investigator. If any results falling outside of these expected normal ranges at the site are deemed not clinically significant by the investigator or an appropriately qualified designee, then this should be clearly stated on the hard copies of the ECG and signed and dated by the investigator.
- If the ECG trace indicates an abnormality that is measured by the equipment but is deemed normal by the investigator, then this should be clearly stated on the ECG tracing as normal and signed and dated by the investigator or appropriately qualified designee. If the ECG tracing indicates an abnormality that is present but deemed as not clinically significant by the investigator or appropriately qualified designee, then this should be clearly stated on the ECG tracing as “NCS” and signed and dated by the investigator or appropriately qualified designee and stored with the source records for that participant. If any results falling outside of the normal ranges are deemed clinically significant by the investigator or appropriately qualified designee then these should be recorded in the eCRF as an AE.
- ECGs will be stored electronically for manual measurement of intervals, if necessary.
- Whenever a 12-lead ECG is scheduled at the same nominal time as other study procedures (including vital signs, blood draws, or meals), the ECG should be obtained first followed by other procedures with timing planned so that the blood draw occurs at the exact nominal time.

8.2.4. Telemetry

Telemetry will be performed during the study as outlined in the SoA. Additional details are available in the SRM.

8.2.5. Holter Monitoring

Cardiac monitoring (24 hour) will be performed using continuous Holter monitoring during the study as shown in the SoA.

Start date and time and stop date and time will be captured in the study database. Analysis of the Holter monitoring will consider the following:

- Heart rate (HR) (brady and tachycardia).
- Normal and aberrant beats.
- Number of supraventricular contractions, premature atrial contractions, supraventricular tachycardias, premature ventricular contractions, couplets, triplets and ventricular tachycardias.
- Atrio-ventricular conduction defects.

- Atrial fibrillation and flutter.

8.2.6. Clinical Safety Laboratory Assessments

- Refer to [Appendix 2](#) for the list of clinical laboratory tests to be performed and to the SoA for the timing and frequency.
- The investigator must review the laboratory report, document this review, and record any clinically relevant changes occurring during the study in the AE section of the CRF. The laboratory reports must be filed with the source documents. Clinically significant abnormal laboratory findings are those which are not associated with the underlying disease, unless judged by the investigator to be more severe than expected for the participant's condition.
- All laboratory tests with values considered clinically significantly abnormal during participation in the study or within 14 days after the last dose of study intervention should be repeated until the values return to normal or Baseline or are no longer considered significantly abnormal by the investigator or medical monitor. Any lab or clinical assessment that is judged to be spurious by the Principal Investigator (PI) may be repeated.
- If such values do not return to normal/Baseline within a period of time judged reasonable by the investigator, the etiology should be identified and the sponsor notified.
- All protocol-required laboratory assessments, as defined in [Appendix 2](#), must be conducted in accordance with the SoA.
- Samples collected for hematology, clinical chemistry, urinalysis, or hormone assays will be analysed at the unit's local laboratory under the relevant Standard Operating Procedures (SOPs), GUIs and user manuals. See user local laboratory manuals for details on methodology, processing, handling of specimens, and analyses.
- Hematology, clinical chemistry, urinalysis and additional parameters to be tested are listed in [Appendix 2](#).

8.2.7. Hormone Monitoring

Based on preclinical findings in the rat Good Laboratory Practice (GLP) toxicology studies outlined in the IB, hormone monitoring will take place in Part B of the study only. Blood samples will be obtained as per the SoA and SRM and analysed for:

- Adrenal – ACTH, cortisol
- Pituitary – LH, FSH, TSH, T3, and free T4
- Total Testosterone and DHT

All laboratory tests with values that are considered clinically significantly abnormal during participation in the study or until the final follow up visit should be repeated until the values return to normal or Baseline or are no longer considered significantly abnormal by the investigator or medical monitor. If such values do not return to normal

within a period judged reasonable by the investigator, the etiology should be identified and the sponsor notified.

8.2.8. Suicidal Ideation and Behaviour Risk Monitoring

Not applicable.

8.3. Adverse Events and Serious Adverse Events

The definitions of an AE or SAE can be found in [Appendix 3](#).

The investigator and any qualified designees are responsible for detecting, documenting, and reporting events that meet the definition of an AE or SAE and remain responsible for following up AEs that are serious, considered related to the study intervention or the study, or that caused the participant to discontinue the study intervention (see Section 7).

8.3.1. Time Period and Frequency for Collecting AE and SAE Information

- All SAEs will be collected from the start of intervention until the follow-up visit at the time points specified in the SoA (Section 1.3). However, any SAEs assessed as related to study participation (e.g., study intervention, protocol-mandated procedures, invasive tests, or change in existing therapy) or related to a GSK product will be recorded from the time a participant consents to participate in the study.
- All AEs will be collected from the start of intervention until the follow-up visit at the time points specified in the SoA (Section 1.3).
- Medical occurrences that begin before the start of study intervention but after obtaining informed consent will be recorded on the Medical History/Current Medical Conditions section of the CRF not the AE section.
- All SAEs will be recorded and reported to the sponsor or designee immediately and under no circumstance should this exceed 24 hours, as indicated in [Appendix 3](#). The investigator will submit any updated SAE data to the sponsor within 24 hours of it being available.
- Investigators are not obligated to actively seek AEs or SAEs after the conclusion of the study participation. However, if the investigator learns of any SAE, including a death, at any time after a participant has been discharged from the study, and he/she considers the event to be reasonably related to the study intervention or study participation, the investigator must promptly notify the sponsor.

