Procedure	Screening (up to 30 days before Day 1)	Intervention Period [Days] (for each dosing cohort)															E.D	Follow-up (~14±1 days post last dose)	Notes E.D = early discontinuation/withdrawal
		-2	-1	1	2	3	4	5	6	7	8	9	10	11	12	13			
Muscle Biopsy			X ¹⁴													X ¹⁵		(X)	Muscle biopsies must be performed AFTER clinical safety assessments on the corresponding days ¹⁴ Day -1 muscle biopsy to occur 1-6 hr after estimated timing of initial dose on Day 1. Time of sample collection to be recorded ¹⁵ Day 10 muscle biopsy to occur within 1-6 hr after last dose administered Time of sample collection to be recorded. Muscle biopsy can be performed at any time during pre-dose period.
Discharge from Clinical Unit																	X	(X)	

- The time to start the second dose in Part B can be modified based on the estimates of half-life from Part A.
- Duration of dosing in Part B can be modified based on the estimates of half-life from Part A.
- The timing and number of planned study assessments, including safety, PK, PD/biomarker or other assessments may be altered during the course of the study based on newly available data (e.g., to obtain data closer to the time of peak plasma concentrations) to ensure appropriate monitoring.
- Any changes in the timing or addition of time points for any planned study assessments as the result of emerging pharmacokinetic/pharmacodynamic data from this study must be documented and approved by the relevant study team member and then archived in the sponsor and site study files, but will not constitute a protocol amendment. The CA and EC will be informed of any safety issues that constitute a substantial amendment and require alteration of the safety monitoring scheme or amendment of the ICF. The changes will be approved by the CA and the EC before implementation.

Part C- Food Effect									
	Screening (up to 30 days before Day 1)	Treatment Period [Days] (with or without food)					E.D.	Follow- up (~14±1 days post last dose)	Notes E.D = early discontinuation/withdrawal
		-1	1	2	3	4			
Informed consent	X								
Inclusion and exclusion criteria (including drug screens)	X		X						Recheck clinical status before randomization and/or 1st dose of study medication.
Demography	X								
Physical examination including height and weight	F	B				B	(B)	F	F: Full exam; B: Brief Exam; height is only taken once at screening

Part C- Food Effect									

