
this clinical study will use micronized, thus there is a risk that the clinical PK will be different than predicted
	
impurity profile of the micronized material was consistent with that of the non-micronized material. Thus, the nonclinical safety data is considered supportive of clinical use of micronized compound.
	
below the dog NOAEL exposure margins, 110- and 270-fold lower for AUC(0-inf) and Cmax, respectively.
 
The suspension used for non-clinical studies was homogenised and the particle size thus reduced smaller than non-micronised. Solubility does not change on micronisation but in-vitro bio-relevant dissolution data shows a proportional response in rate of dissolution for non-micronised, ground and micronized.

Study Procedures		

Entero-Test
 
Streaks of blood on the string due to local irritation have been infrequently noted. Rarely, a patient will be unable to swallow the capsule because of gagging or will vomit after doing so. Gagging upon retrieval of the string can occur. On a few occasions, an entire string has been swallowed without ill effects
		
The use of Entero-Test has been approved by the FDA (510(k), Summary of safety and effectiveness). The string will be securely taped in place during the collection time to minimize risk of swallowing the entire string. Any subject incapable of swallowing the capsule will be allowed to participate in the study without duodenal bile collection.

Potential Risk of Clinical Significance	Summary of Data/Rationale for Risk	Mitigation Strategy
and passes from the body in the feces. Consider risks associated with comparators, challenge agents, imaging agents, medical devices, etc		

Muscle Biopsy
 
Localized pain from muscle biopsy procedure can occur
 
Low risk of bleeding or infection could occur as result of the procedure. There is a very low risk of nerve damage as a result of the procedure
		
Local anesthetic will be employed during muscle biopsy procedures.
 
Acetaminophen or another medication selected by the investigator and the medical monitor can be administered to participants to control post-procedural pain.
 
Biopsy procedure will be performed by staff experienced in the technique. Participants will be followed up for any adverse events resulting from the biopsy and managed appropriately, if needed.

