5.2. Baseline Definitions

For all endpoints (except as noted in baseline definitions) the baseline value will be the latest pre-dose assessment with a non-missing value, including those from unscheduled visits. For the parameters having multiple assessments, mean value of the assessments will be considered as baseline value.

Baseline Definitions – Part A

Parameter	Study Assessments Considered as Baseline				Baseline Used in Data Display
	Screening	Day -2	Day -1	Day 1 (Pre-Dose)	
Safety Assessments					
Lab results, 12-lead Electrocardiogram (ECG) & Vital Signs	X	X		X	Day 1
Routine Urinalysis	X			X	Day 1
Telemetry				X	Day 1 30 min (\pm 10 min)
Pharmacodynamics parameters			X	X	Day -1 #

Postdose value will be collected on intervals 0-2, 2-4, 4-6, 6-8, 8-12 and 12-24 hr. Time matched predose value for each of these intervals (24-22, 22-20, 20-18, 18-16, 16-12 and 12-0 respectively), predose aggregate value of 24-12hr (for post dose aggregate of 0-12 hrs) and predose aggregate value of 12-0 hr (for post dose aggregate of 12-24 hrs) will be considered as baseline for different pharmacodynamic parameters

Baseline Definitions – Part B

Parameter	Study Assessments Considered as Baseline				Baseline Used in Data Display
	Screening	Day -2	Day -1	Day 1 (Pre-Dose)	
Safety Assessments					
Lab results	X	X	X	X	Day 1
Hormone monitoring			X		Day -1 [†]
Routine Urinalysis, 12-lead Electrocardiogram (ECG) & Vital Signs	X	X		X	Day 1
Telemetry				X	Day 1 30 min (\pm 10 min)
Pharmacodynamics parameters			X	X	Day -1 #
Blood sampling for metabolite profiling				X	Day 1 (pre-dose)
Muscle Biopsy			X		Day -1

[†] There will be 2 individual baseline values (samples from midnight and 9am) for ACTH and Cortisol hormones. Both values may be used to calculate change from baseline for post dose measurements.

Postdose value will be collected on intervals 0-2, 2-4, 4-6, 6-8, 8-12 and 12-24hr. Time matched predose value for each of these intervals (24-22, 22-20, 20-18, 18-16, 16-12 and 12-0 respectively), predose aggregate value of 24-12hr (for post dose aggregate of 0-12 hrs) and predose aggregate value of 12-0 hr (for post dose aggregate of 12-24 hrs) will be considered as baseline for different pharmacodynamic parameters

Baseline Definitions – Part C

Parameter	Study Assessments Considered as Baseline			Baseline Used in Data Display
	Screening	Day -1	Day 1 (Pre-Dose)	
Safety Assessments				
Lab results, 12-lead Electrocardiogram (ECG) & Vital Signs	X		X	Day 1

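### Part B: non-serious complications of the Day -1 muscle biopsy that begin and are noted before the first dose are filed as medical history, so they miss the AE tables and listings

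*Protocol*

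**What the plan says.** Protocol 8.3.1 opens the window for non-serious events at dosing: "All AEs will be collected from the start of intervention until the follow-up visit at the time points specified in the SoA". For anything earlier it says "Medical occurrences that begin before the start of study intervention but after obtaining informed consent will be recorded on the Medical History/Current Medical Conditions", and it expressly rules out the AE page. The one exception is for serious events. SAEs judged related to study participation, including required procedures and invasive tests, "will be recorded from the time a participant consents to participate in the study".

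The Part B biopsies fall on either side of that boundary. The 7-day schedule in Protocol 1.3 has the note "Day -1 muscle biopsy to occur 1-6 hr after estimated timing of initial dose on Day 1" and places the second biopsy 1 to 6 hours after the last dose. Protocol 4.1 describes a pre-dose and a post-dose biopsy for Part B generally. SAP 5.2 gives Day -1 as the muscle biopsy baseline.

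The risk table in Protocol 2.3.1 names pain, bleeding, infection and nerve damage as biopsy risks. Its mitigation entry reads: "Participants will be followed up for any adverse events resulting from the biopsy and managed appropriately, if needed". It does not limit this to serious events or to events after dosing.

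**The concern.** Safety and tolerability is a primary objective, and the biopsy is an invasive procedure that participants undergo only because the protocol requires it. The two biopsies carry the same named risks but fall under different recording rules. A haematoma or numbness that appears on the evening of Day -1 is entered as history. The same finding on the evening of the second biopsy is an AE.

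What is at stake is how fully the study describes its own procedural risk. The first biopsy will tend to look cleaner than the second because of where the AE window opens. The AE outputs would also not fully show the events that the risk table says will be followed.

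**Working it through.** The plan states no figure on this point, so the check is a comparison of sections with a little arithmetic.

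1. **Sorting rule.** Protocol 8.3.1 sorts by onset relative to the first dose. Protocol 10.3.1 ties the AE definition to use of study intervention. It also counts as AEs new conditions first detected after dosing even if they were present before, and worsening of a pre-existing condition. The events excluded are therefore those that begin before the first dose, are noted before it, and do not worsen afterwards.

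2. **Length of the window.** I read the schedule note as the dosing clock time on Day -1 plus 1 to 6 hours, with the first dose at that clock time on Day 1. Gap = 24 h minus the hours after the dosing clock time: 24 - 6 = 18 h and 24 - 1 = 23 h. The same note also allows the biopsy at any time in the pre-dose period, so individual gaps may differ.

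3. **Scheduled recording of history.** In both Part B schedules, medical history and past/current conditions are collected at screening and Day -2, and the history row covers changes up to admission. The order is Day -2 (history), Day -1 (biopsy), Day 1 (dose). No scheduled history collection lies between biopsy and dose.

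4. **Where such an event is reported.** If recorded, it can appear in SAP Table 1.28 (a study population table) and Listing 33 (medical conditions). It cannot appear in AE Tables 3.1 to 3.16 or the AE listings. None of those AE tables separates procedure-related events.

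5. **The second biopsy.** It follows the last dose by 1 to 6 hours in the 7-day schedule. AE collection runs to the follow-up visit, and the on-treatment phase in SAP 13.4.1 runs to the stop date plus 3 days. A complication soon after this biopsy is an on-treatment AE.

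| Biopsy-related event | First biopsy: begins and noted before dose | First biopsy: begins, first detected or worsens after dose | Second biopsy |
|---|---|---|---|
| Non-serious | Medical history | AE | AE |
| Serious | SAE, from consent | SAE | SAE |

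Only one cell of the six differs.

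6. **Extent.** 3 cohorts x about 12 participants = about 36 first biopsies, each followed by this window. The documents give no biopsy complication rate and no distribution of onset times, so the number of events lost cannot be computed.

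**The case against.** The strongest reply is that this is a deliberate AE window covering about one day of minor, known, monitored events before any drug is given. The follow-up wording in 2.3.1 sits in a mitigation column and can be read as clinical care, not as a promise of an AE form. Participants are resident from Day -2, so that care happens whichever form is used. Serious biopsy events are captured from consent. Treated pain leaves a trace, because Protocol 6.5 requires the reason for any medication. Much of this stands. It shows that the gap is narrow and that care is not in question. It does not explain why 8.3.1 treats procedure-related events as recordable from consent when serious but not when non-serious, or where the non-serious ones would be recorded on schedule.

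A reader might infer four stronger things that the documents do not support.

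- **That half of biopsy complications are lost.** With two biopsies each there are 36 x 2 = 72, of which 36 (50%) are pre-dose. That is a share of procedures. Complications with later onset, such as many wound infections, are still AEs.
- **That a procedure effect could pass for a drug effect.** Each cohort has concurrent randomised placebo participants (about 3 of 12) on the same biopsy schedule. Safety is compared descriptively with placebo, and no within-participant comparison of the two biopsies is planned.
- **That the withdrawal rule in 7.1.3 makes the gap consequential.** The second biopsy follows the last dose, so a misattributed event after it cannot cost that participant further dosing.
- **That the events vanish from the study altogether.** They are assigned to a CRF section with its own table and listing. What they miss is the AE output.

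**Conclusion.** The point holds in a narrow form. Non-serious complications of the Day -1 biopsy that begin and are noted before the first dose are kept out of the AE record, and no scheduled history collection follows the biopsy to pick them up. The procedural risk of the first biopsy is therefore under-recorded relative to the second. About 36 participants each pass through a window of roughly 18 to 23 hours. The count of affected events is unknown and may be small. The drug-placebo comparison is not biased, because the first biopsy precedes dosing in both arms.

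This rests on two assumptions: that the timing note means the dosing clock time on Day -1, and that the 14-day cohorts follow the same timing. For those cohorts the Day -1 biopsy itself is supported by Protocol 4.1 and SAP 5.2. The change is a worthwhile, inexpensive improvement to a primary safety record. It does not correct an invalid analysis.

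**What to change.** - **Protocol 8.3.1:** add a sentence that, in Part B, non-serious events related to a protocol-mandated procedure are recorded as AEs from the Day -1 biopsy onward, with a procedure-related flag. Add a matching clause to the AE definition in 10.3.1, which is now tied to study intervention.
- **Both Part B schedules:** start AE review at the Day -1 biopsy.
- **SAP:** report these events under the existing pre-treatment phase in Table 3.3, the Part B AE table by study phase, separate from post-dose AEs. SAP 13.4.1 puts every date up to and including the treatment start date in that phase, so use onset time or the flag to keep Day 1 post-dose events out of it.

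No visit or procedure is added, since participants are already in the unit from Day -2. The cost is a few lines of text, one CRF flag, a small change to one display and a few more recorded AEs.
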